6.1 Statistical methodology

This study will be a randomized controlled trial of navigation bronchoscopy vs. CT-guided biopsy using a non-inferiority study design. The hypothesis of the study is that the diagnostic accuracy of EMN navigation bronchoscopy using the SuperDimension platform with F-Nav performed by interventional pulmonologists is non-inferior to the diagnostic accuracy of CT-guided biopsy performed by interventional radiologists. Eligible patients will be randomized on a 1:1 basis and the randomization will be stratified by the following two criteria within each center to provide balance between treatment arms on these features:

1. Location in the middle or outer third of the lung
2. Pre-test probability of malignancy (50% or less VS 51% or more)

Within each stratum, block sizes of 2 and 4 will be used to enhance blinding.

Though the primary analysis will use a Bayesian approach, the initial power analysis uses a Frequentist approach. We assume that a diagnostic accuracy for CT-guided biopsy is 90%. The non-inferiority margin is set at 10 percentage points, and one-sided type I error rate is set at 5%. Thus, if the true diagnostic accuracy for navigation bronchoscopy is lower than 80%, we will have 5% probability (type I error rate) to incorrectly conclude noninferiority. With this parameter setting a sample size of 112 per group will give approximately 80% power if the true diagnostic accuracies are 90% for both arms. Considering an attrition rate of 15%, the sample size is 129 per group (258 total). Large volume centers could be expected to enroll 50 patients per year, therefore 6 centers are necessary. One year recruitment plus one year follow-up represents 2 years of recruitment time. The noninferiority margin has been chosen based on the known pneumothorax rate of CT

CONFIDENTIAL

biopsy which is in excess of 10%, and after polling a number of clinicians who are involved in the diagnostic workup of patients with lung nodules, where this margin was considered reasonable.

6.2 Analysis plan

Analytic populations

The analysis set will be the per-protocol (PP) population, which yields more conservative estimates for the noninferiority objective than the intention-to-treat (ITT) population. The ITT analysis will include every randomized subject assigning a treatment failure for those who drops out without the final data. The ITT analysis will be a secondary, sensitivity analysis.

Prior distribution

The probability of successful diagnostic accuracy for each treatment arm will be modeled with a Beta-Binomial distribution. A non-informative prior Beta (1,1) will be used for both treatment arms.

Interim analysis

No interim analysis is planned for this trial. Interim analyses typically assess for futility and efficacy stops regarding the primary outcome part-way through a trial. However, the primary outcome of diagnostic accuracy requires up to 12 months of radiographic follow-up in patients not determined to have malignant nodules by study biopsy. Therefore, an analysis of this outcome halfway through accrual could not be performed until one year after that enrollment midpoint was reached, at which time we expect enrollment to be complete for the entire planned accrual. An interim analysis of the primary endpoint is therefore impracticable. Interim analyses for safety endpoints are often commonly performed in investigations of new devices or novel interventions, but as both study procedures represent long-standing standard of care options for the tissue sampling of lung nodules, complications of these procedures themselves are not considered risks unique to this research. The primary risk to participation in this research involves patient privacy and confidentiality, any breach of which will be reported to the PI and appropriate regulators on an ongoing basis as described later in this protocol, which does not require interim analysis.

Final analysis

The final analysis will be conducted when data from all randomized patients are available (n=112 per group). The conclusion will be based on the final posterior distributions (n=112 each). We will conclude noninferiority of NB compared to CT if the estimated probability of inferiority is less than 5%. We will conclude superiority of NB if the estimated probability that NB is better than CT is higher than 95%.

The median estimate and 95% credible interval will be given for the diagnostic accuracy for NB and for CT, as well as their difference. Additionally, we will estimate and report the probability that NB is non-inferior to CT and NB is superior to CT. These probabilities can be estimated using the posterior distributions of diagnostic accuracies.

Subgroup analysis:

CONFIDENTIAL

Pre-hoc analyses of subgroups will include the groups defined by the two stratification factors, expertise of radiologist or pulmonologists, etc... The full list of subgroup pre-hoc analyses will be defined in the statistical analysis plan which will be completed and signed off by the trial steering committee prior to final patient entry and prior to any prior full analysis of the data. To allow for comparison of diagnostic accuracy and yield differences across subgroups (e.g., middle vs outer third), logistic regression models with interaction with treatment group will be fit.

Operating characteristics

With the Bayesian paradigm, there is no type I error rate. We conducted a simulation study to determine appropriate threshold for noninferiority conclusion and superiority conclusion at the final analysis. The operating characteristics of the proposed design under various scenarios for the true unknown parameter distributions were evaluated and shown in the below table. In this simulation study, we first postulated the true distribution of the diagnostic accuracy using a Beta distribution, which gives the specific mean and standard deviation. For example, Beta(141, 35) is used to represent a distribution with mean 0.80 and standard deviation (sd) 0.03. We used 0.60, 0.70, 0.80, and 0.90 as the mean and 0.01 and 0.03 as the sd. However, because different standard deviations yielded similar results, we only present the results for sd=0.03. The simulation size is 10,000 and the available decision in the simulation is: conclude non-inferiority at final analysis (> -10%). The following table shows its probability under various scenarios.

Design characteristics with final 10% (0.95)

True CT Mean	True NB Mean	True State	Difference	Final analysis		
				NB is non-inferior	NB is superior	
0.7	0.6	Inferiority	-0.1		5.3	--
0.8	0.7	Inferiority	-0.1		4.7	--
0.9	0.8	Inferiority	-0.1		5.4	--
0.8	0.6	Inferiority	-0.2		--	--
0.9	0.7	Inferiority	-0.2		--	--
0.7	0.7	Non-inferiority	0.0		44.9	4.9
0.8	0.8	Non-inferiority	0.0		54.2	4.9
0.9	0.9	Non-inferiority	0.0		74.4	4.7
0.6	0.7	Superiority	0.1		47.0	46.5
0.7	0.8	Superiority	0.1		43.7	53.0
0.8	0.9	Superiority	0.1		31.7	67.8
0.6	0.8	Superiority	0.2		4.8	95.1
0.7	0.9	Superiority	0.2		1.3	98.7

Probabilities less than 1% are not shown.

CONFIDENTIAL

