4.7 Comparison: CT-guided Biopsy Pathway

The control arm of the study will consist of CT-guided biopsy, which will be performed by interventional radiologists with expertise in transthoracic needle biopsy and/or fine needle aspiration (as defined by more than 25 procedures performed in the past two years as a department). Procedures will be performed in a dedicated interventional CT scanner with multi-slice capabilities. Patient analgesia with local anesthesia and moderate conscious sedation will be used. Biopsy number, core biopsy vs. fine needle aspiration, use of coaxial needles, and use of rapid on-site cytologic examination will be at the discretion of the proceduralist per local institutional preferences. Procedures will be followed by limited CT scan and/or chest radiograph to exclude pneumothorax if required per local standard of care. The procedure will be deemed non-diagnostic if the proceduralist is unable to reach the nodule or if a complication occurs and therefore no biopsy is obtained.

- 1. Patients not eligible for general deep sedation and general anesthesia and therefore not eligible for bronchoscopy, but potentially eligible for CT-guided biopsy, will be excluded from the study but recorded as such in the CONSORT diagram.**
- 2. Patients randomized who fail to present for their assigned intervention will be considered screen-failure**
- 3. Patients randomized who present for their assigned intervention but do not undergo the procedure for reasons other than for contraindications to the procedure (per institutional policy) will be analyzed as non-diagnostic procedure, and otherwise considered screen-failure. The cause for cancellation will be recorded in the case report form.**

CONFIDENTIAL

See Procedural Flow Chart (Section 14).

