Please contact the assigned Study Contact with any questions regarding this process. You can also reach out to your assigned CRA once the study is activated.

The VICC Coordinating Center will assign Subject ID numbers to all patients whose eligibility has been confirmed. Only patients deemed eligible will be registered to the study. Sequence/study ID numbers will not be re-used if a patient screen fails. Following registration, eligible participants should begin the study consistent with the protocol no later than 28 days after registration/enrollment by the VICC Coordinating Center.

Following registration, eligible participants should initiate navigation bronchoscopy or CT-guided biopsy no later than 30 business days after the site is notified of randomization by the VICC Coordinating Center. If a participant does not receive the procedure following randomization within the allowed time period, the patient may be re-consented or participant's registration on the study will be canceled. The Study Contact should be notified of cancellations as soon as possible.

The purpose of this 30 business day scheduling window is to protect subjects from being randomized to a procedure which overly delays their care, when the alternative procedure could be performed substantially sooner and would otherwise have been utilized in clinical practice outside of this trial. For example, if biopsy procedure #1 cannot be performed for 8 weeks due to local factors (equipment failure, perhaps), but biopsy procedure #2 could be performed within two weeks, the 30-day window protects this patient from a potentially harmful delay in a malignant diagnosis by removing them from the trial so they may proceed with procedure #2 on clinical grounds. However, if a situation arises in which a patient must be scheduled outside the 30-day window but 1) the alternative procedure cannot be performed meaningfully sooner and 2) the delay in biopsy is

CONFIDENTIAL

not expected to impact any eligibility criteria, the patient may remain in the trial (an example in which point #2 might be invoked: a patient with a 29 mm nodule delayed for 3 months, a sufficiently long interval of time in which the nodule may well have grown to exceed 30 mm diameter and therefore no longer be eligible for the trial). This determination must be agreed upon by both the local PI and the central PI ([name]) and will be documented in the "notes" field at the end of REDCap CRF #1.

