As is generally accepted, standard of care procedures performed prior to consent, but within the protocol defined screening window for each assessment, can be used for study purposes. All research-only procedures must be performed after patient consent.

Subjects who provide informed consent, but are determined to be ineligible prior to initiation of navigation bronchoscopy or CT-guided biopsy will be considered screen failures and the reason for screen failure will be documented. Subjects who fail to present to their assigned procedure after randomization will be considered screen failures as well. Subjects who present to their assigned procedure but do not undergo the procedure for reasons other than safety will be analyzed on an intention-to-treat basis (see above Section 4.7 for details).

6. Methodology

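### The per-protocol set that decides non-inferiority has no visible definition, and an ITT set of all randomised patients conflicts with rules that relabel, cancel or remove some of them

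*Combined protocol and SAP*

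**What the plan says.** Section 6.2 (Analytic populations) states: "The analysis set will be the per-protocol (PP) population, which yields more conservative estimates for the noninferiority objective than the intention-to-treat (ITT) population". ITT is a secondary, sensitivity analysis: "The ITT analysis will include every randomized subject assigning a treatment failure for those who drops out without the final data". No visible text lists who belongs to the per-protocol (PP) set. The subgroup paragraph of Section 6.2 mentions a statistical analysis plan to be signed off before the last patient enters, but assigns it only the subgroup list.

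Other sections deal with patients who do not get the assigned procedure:

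- **No-shows.** Section 4.7: "Patients randomized who fail to present for their assigned intervention will be considered screen-failure". Section 5: "Subjects who fail to present to their assigned procedure after randomization will be considered screen failures as well".
- **Present but not done.** In Section 4.7, those untreated for a reason other than a contraindication "will be analyzed as non-diagnostic procedure, and otherwise considered screen-failure". In Section 5, those who present but "do not undergo the procedure for reasons other than safety will be analyzed on an intention-to-treat basis", with a reference back to Section 4.7.
- **Found ineligible.** Section 5: consented patients "determined to be ineligible prior to initiation of navigation bronchoscopy or CT-guided biopsy will be considered screen failures".
- **Window missed.** Section 5: the patient may be re-consented, or the participant's "registration on the study will be canceled". The stated purpose is to take a patient out of the trial when the assigned procedure is late and the other could be done sooner. A patient may stay if the other procedure is not meaningfully sooner and eligibility is not expected to change, by agreement of the local and central principal investigators.

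Under Sections 4.6 and 4.7, a procedure that fails to reach the nodule, or yields no biopsy because of a complication, is scored non-diagnostic in both arms.

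**The concern.** Two analysts following this text could build different denominators for both sets. For PP there is no membership rule to apply. For ITT, Section 6.2 points one way and the screen-failure, cancellation and removal rules point another.

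The window rule matters most. Whether a patient is removed depends on how soon the other procedure is available, and that is judged after randomisation with the allocation known. Membership of the deciding set can therefore depend on the arm. The planned reassurance, that PP is the stricter set, would hold only under particular patterns of loss.

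**Working it through.** **1. The texts side by side.**

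| Randomised patient | Sections 4.7 and 5 | Section 6.2, ITT | PP |
|---|---|---|---|
| Does not present | screen failure | included, failure | not stated |
| Cancelled, contraindication (4.7) or safety (5) | screen failure | included, failure | not stated |
| Present, not done, other reason | non-diagnostic (4.7); ITT basis (5) | included, failure | not stated |
| Ineligibility found after randomisation | screen failure, if the rule reaches them | included, failure | not stated |
| Window missed | re-consented, cancelled or removed | included, failure | not stated |

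The ITT column takes Section 6.2 literally. No text reconciles it with the second column or says how a re-consented patient is counted.

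**2. Reproducing the plan.** Inputs from Section 6.1: 90% in both arms, margin 10 points, one-sided 5%, 80% power.

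n = (1.645 + 0.842)² × 2 × 0.9 × 0.1 / 0.10² = 111.3, so 112 per arm. Then 112 × 1.15 = 128.8, so 129. Both match.

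Rule (Section 6.2): conclude non-inferiority if P(pN − pC < −0.10 | data) < 0.05, with independent posteriors Beta(1 + x, 1 + n − x). The probability of meeting it is the sum, over all pairs of success counts, of the two binomial probabilities wherever the rule is met. At 112 per arm with fixed true rates this gives 80.1% at 90/90 and 5.3% at CT 90%, NB 80%. The plan's table gives 74.4 + 4.7 = 79.1% and 5.4%. At 129 per arm the figures are 84.8% and 5.3%.

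**3. Removals unrelated to outcome** (129 randomised per arm; true CT 90%, NB 80%; counts assumed). Error is the probability of wrongly concluding non-inferiority.

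| Removed | PP error | ITT error, removed = failure |
|---|---|---|
| 3 NB only | 5.4% | 1.8% |
| 6 NB only | 5.3% | 0.5% |
| 3 CT only | 5.3% | 11.5% |
| 15% of both arms, independent per patient | 5.3% | 8.9% |
| exactly 19 per arm | 5.3% | 3.3% |

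In the fourth row failure scoring shrinks the true rates to 0.80 × 0.85 = 0.68 and 0.90 × 0.85 = 0.765. The difference becomes 8.5 points, inside the margin, so error rises. In the last row the mean difference is about the same, but a fixed number of failures makes the observed counts vary less than the rule assumes, so error falls. Which set is stricter therefore depends on which arm loses patients and on how loss is modelled.

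**4. Removals related to outcome.** If k NB patients leave and half would have failed, the retained NB rate is (0.80 × 129 − 0.5k)/(129 − k).

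- k = 3: 101.7/126 = 0.807; PP error 7.4%.
- k = 6: 100.2/123 = 0.815; PP error 9.8%.

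If only would-be CT failures leave, PP error falls instead, to about 2% with 3 and under 1% with 6.

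**5. Single data sets near the boundary.** NB 110/129 v CT 116/129 has probability of inferiority 0.094 and fails; if 3 NB failures leave, 110/126 gives 0.034 and passes. NB 112/129 v CT 116/129 gives 0.043 and passes; if 3 CT failures leave, 112/129 v 116/126 gives 0.105 and fails. These were chosen close to 0.05 to show that a few patients can matter in either direction.

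**The case against.** A reader might infer that ITT will leave these patients out. The documents do not establish that. Read literally, Section 6.2 includes and scores every randomised patient, and the ITT phrase in Section 5 refers back to Section 4.7, so it may be only a scoring rule for those who present and are not done. What stands is an unreconciled conflict, not a stated omission.

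A reader might also take the ineligibility rule as a removal of randomised patients. It covers consented patients, and central adjudication comes after consent and before randomisation, so many of them were never randomised. It can still reach some who were.

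It is tempting to quote the result if every removed NB patient would have failed: error of 12% with 3 and 24% with 6. For removals made before any biopsy this is an extreme bound. At 80% accuracy, three patients unselected for outcome would all fail with probability 0.2³ = 0.8%, and six with 0.2⁶ = 0.006%. The only removal example in Section 5, equipment failure, has no evident link to outcome, and PP error then stays near 5%.

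In fairness to the plan, PP is the stricter set under independent equal loss (5.3% v 8.9%). Attempted procedures that fail are scored alike in both arms, so the exposure is removals before the procedure and any later PP exclusions. The CONSORT and flow-chart figures are not shown in the text available, so a rule drawn only there cannot be excluded. None of this supplies a PP definition or settles the conflict.

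**Conclusion.** The point holds and should be fixed. The deciding set has no visible definition, stated rules allow exclusions after randomisation with the arm known, and the back-up set conflicts with those rules. The claim that PP is more conservative is true under some loss patterns and false under others.

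The size and direction of any bias are unknown. PP error does not move if removals are unrelated to outcome. It rises by roughly 2 to 5 points (5.3% to 7.4% or 9.8%) in the half-failure illustration with 3 or 6 NB removals, and falls if CT failures are the ones removed. Failure-scored ITT can itself favour either arm. These results rest on assumed removal counts, true rates of 90% and 80%, and 129 randomised per arm. The documents give no removal rates by arm.

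**What to change.** 1. Keep every randomised patient in the ITT analysis under the assigned arm. Do not apply screen-failure or cancellation labels after randomisation for analysis purposes. Amend Sections 4.7 and 5 to agree with 6.2.
2. Define PP membership before outcomes are known, by rules that do not depend on the biopsy result. For each category (no-show, cancelled, found ineligible after randomisation, window missed, re-consented, present but not done) state whether it enters PP and how it is scored in each set.
3. Report ITT beside PP, with removals by arm and reason. Because failure scoring favours NB when removals fall mainly on CT, add one run with removed NB patients as failures and removed CT patients as successes. Use it as a robustness report only: as a decision rule it would cut power at 90/90 to 64% with 3 removed per arm and 37% with 6.
4. Delete the unconditional claim that PP is more conservative.
5. Reconcile the passages that decide who is removed. Section 4.5 equates 3 weeks (21 days) with 30 calendar days. Section 5 gives 30 business days (30 × 7/5 = 42 calendar days) and, from registration, 28 days. Section 4.7 exempts contraindications where Section 5 exempts safety. Which clinical rule is right is for the investigators.

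The cost is wording and a few analysis runs. Consent creates a database record before randomisation (Section 5) and exit reasons are documented (Section 4.3), so the all-randomised set can be built. The PP decision rule and its power are unchanged (83.5% at 90/90 with 3 per arm removed at random).

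### The ITT sensitivity analysis scores dropouts as failures in both arms; with balanced dropout this narrows a true deficit against a fixed 10-point margin and also costs power

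*Combined protocol and SAP*

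**What the plan says.** Section 6.2 (Analytic populations) sets the primary population: "The analysis set will be the per-protocol (PP) population, which yields more conservative estimates for the noninferiority objective than the intention-to-treat (ITT) population". It then defines the alternative: "The ITT analysis will include every randomized subject assigning a treatment failure for those who drops out without the final data". Its role is stated next: "The ITT analysis will be a secondary, sensitivity analysis". No arm is exempt from the failure rule. No other sensitivity analysis of the primary endpoint and no other handling of missing outcomes is given. The operating-characteristics table in 6.2 has no attrition scenario.

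Section 6.1 assumes 90% accuracy for CT-guided biopsy, a 10-point margin and a one-sided 5% error rate. It says that "a sample size of 112 per group will give approximately 80% power" when both arms are at 90%, and raises 112 to 129 per group for a single attrition rate of 15%. The margin is justified for diagnostic accuracy.

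**The concern.** Scoring missing outcomes as failures is often thought of as cautious. In a non-inferiority comparison it need not be. Adding the same proportion of failures to both arms draws the two rates together, and similarity is what the trial sets out to show. It also moves both rates away from 90% towards values with larger binomial variance, so a truly equivalent procedure is more likely to fail the test.

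What is at stake is the value of the check. The primary analysis drops patients after randomisation, and this is the only stated analysis that puts them back. Under balanced dropout it is somewhat too easy to pass when NB is 10 points worse and too hard to pass when the arms are equal.

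**Working it through.** **Inputs.** From 6.1: CT 90%; NB 80% at the boundary; margin 10 points; one-sided 5%; 112 per group raised to 129; attrition 15%. From 6.2: Beta(1,1) priors; non-inferiority concluded if the posterior probability of inferiority is below 5%. The documents give neither attrition by arm nor the share of malignant nodules, so both are assumed below.

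**1. The plan's own figures.** n = (1.645 + 0.842)² × (0.9×0.1 + 0.9×0.1) / 0.10² = 111.3, so 112. Then 112 × 1.15 = 128.8, so 129. Exact enumeration of the Bayesian rule at 112 per arm gives 5.3% false non-inferiority at 90/80 and 80.1% power at 90/90. The table in 6.2 gives 5.4%, and 74.4 + 4.7 = 79.1%. With 129 × 0.85 ≈ 110 completers per arm and no failure scoring, the results are 5.3% and 78.9%. These are the fair comparators.

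**2. Upper case: attrition d equal in both arms and unrelated to outcome.** Each success rate is multiplied by (1-d). At d = 15%, 90% v 80% becomes 76.5% v 68.0%, a gap of 8.5 points. At 90/90 the variance term rises from 0.9×0.1 = 0.09 to 0.765×0.235 = 0.18. Exact enumeration at 129 per arm:

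| d | Gap at boundary (points) | False non-inferiority | Power at 90/90 |
|---|---|---|---|
| 0 | 10.0 | 5.3% | 84.8% |
| 5% | 9.5 | 6.4% | 73.9% |
| 10% | 9.0 | 7.5% | 66.2% |
| 15% | 8.5 | 8.9% | 60.4% |

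A normal approximation gives 8.5% and 59.8% in the last row.

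**3. Who actually loses a success.** The rule applies only to dropouts without final data. Under 4.8, malignant histology is a success at biopsy and a non-diagnostic biopsy is already a failure. Successes are therefore lost mainly among specific benign findings awaiting the 12-month status. Suppose 15% drop out regardless of biopsy result, accuracy is equal in malignant and benign nodules, and a share q is malignant. The effective loss is then 0.15(1-q):

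- q = 40%: loss 9%, false non-inferiority 7.3%, power 68%.
- q = 80%: loss 3%, false non-inferiority 6.0%, power 78%.

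If instead the whole 15% (in the CT arm) fell on patients without malignant histology, the figures would be about 8.6% to 7.7% and 61% to 65%. That requires 23% to 54% dropout within that group.

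**4. Balance between arms.** The gap at the boundary stays at 10 points when 0.9 × d(CT) = 0.8 × d(NB), that is, when d(NB) = 1.125 × d(CT). At an average of 15% this is 15.9% v 14.1%. Using the step 2 model at 129 per arm:

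| CT dropout | NB dropout | False non-inferiority | Power at 90/90 |
|---|---|---|---|
| 14% | 16% | 4.9% | 47% |
| 10% | 20% | 0.2% | 8% |
| 16% | 14% | 14.8% | 73% |
| 20% | 10% | 56.8% | 98% |

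At lower attrition, CT 5% v NB 6% gives 4.6%. If both arms lose the same absolute number of success points, false non-inferiority stays near 5% and only power falls.

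**The case against.** **The plan already discounts this analysis.** It is secondary, and 6.2 itself calls the per-protocol set the more conservative one. This stands. A reader might take 8.9% as the trial's false-claim rate, or suppose that a per-protocol success must be confirmed by ITT. The documents support neither: the conclusion rests on the per-protocol posterior, and no section requires the two analyses to agree. If agreement were required, a second hurdle could only lower the false-claim rate. Nor is the sample size tied to the ITT rule, so its lower power breaks no stated commitment.

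**The direction is not fixed.** This also stands. A reader might infer that the rule always favours non-inferiority, or that it is useless as a check. Step 4 contradicts both. Failure scoring reacts sharply to excess NB dropout, which a per-protocol analysis would hide. But a two-point imbalance either way changes the answer materially, which argues for showing the dependence rather than fixing one extreme assumption.

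**Failure scoring fits the endpoint.** Under 4.8 a specific benign finding counts only with absence of malignancy over one year, so an unconfirmed case arguably has no definitive diagnosis. If dropout were meant as part of a composite outcome, the excess over 5% would not be an error for that outcome. The plan does not say so, and the margin in 6.1 was set for accuracy with CT at 90%, not for a composite in which CT could be as low as 76.5%.

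**The power loss can be overstated.** Setting 85% against 60% compares 129 complete patients per arm with 129 of whom 15% drop out. The plan counts on about 80% at 112, so the fair contrast is 79-80% against 60%.

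**Conclusion.** The concern holds conditionally. With dropout about equal and proportional in the two arms, the ITT rule as written leans towards non-inferiority and loses power. The upper case is 8.9% false non-inferiority and about 60% power, against 5.3% and 79-80%. The more realistic range is about 6-7% and 68-78%. That range rests on an assumed malignancy share of 40-80%, equal accuracy in malignant and benign nodules, and 15% dropout unrelated to the biopsy result. An NB dropout rate about one eighth higher than CT cancels the inflation and a larger excess reverses it; more CT dropout makes it worse. The per-protocol primary conclusion is not directly affected. What is weakened is the only stated check on it.

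**What to change.** In 6.2, replace the failure rule with the following:

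1. Keep every randomised patient in the assigned arm and use biopsy results already known: malignant as success, non-diagnostic as failure.
2. Impute only the missing 12-month status, within arm and given the biopsy result.
3. Add a tipping-point analysis that varies the imputed success rate separately by arm, including NB at the CT rate minus 10 points, and report where non-inferiority is lost.
4. Keep the all-failures result as a descriptive line, with dropout counts by arm and biopsy result.

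Step 3 carries most of the value. In 4,000 simulated trials at 15% random attrition, within-arm imputation alone gave about 4.6% false non-inferiority and 79% power, close to the completer analysis. Imputing missing NB outcomes at the CT rate minus 10 points gave about 2.3% and 67%. The same simulation gave 8.1% for all-failures, against 8.9% by enumeration, so these figures are approximate.

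The text should also say how randomised patients with no procedure enter this analysis: 4.7 and 5 call those who fail to present screen failures, while 6.2 includes every randomised subject.

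The cost is wording, a few lines of code and one more sensitivity table. No new data or patients are needed. The separate statistical analysis plan that 6.2 says will be signed off before final patient entry is a natural place for the detail.
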